2.2 Statistical Analysis

Continuous data (e.g. age, BMI, Oxford Shoulder Score) will be reported using mean, standard deviation, median, and range. Comparisons between continuous baseline and interim patient visits will be performed using standard statistical tests and will be chosen as appropriate for the scale and distribution of the measures being analyzed. For example, a t-test, Wilcoxon test, or one-way ANOVA (as appropriate) may be performed to assess differences. Comparisons between preoperative and follow-up visit scores will use two-sided comparisons with $\alpha = 0.05$, with no adjustment for multiple comparisons.

Categorical data (e.g. gender) will be reported using frequency and percentage. Comparisons between categorical baseline and interim patient visits will be performed using standard statistical tests and will be chosen as appropriate for the scale and distribution of the measures being analyzed.

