1 STUDY SYNOPSIS

Complete Protocol Title	ASHCOM [™] Shoulder System and Its Related Instruments A Multicenter, Prospective, Non-Controlled Post Market
	Clinical Follow-up Study
Protocol Number	CME2017-67E
Short Protocol Title	ASHCOM [™] Shoulder System and Its Related Instruments
Sponsor	Zimmer GmbH, [name]
Manufacturer	Zimmer Switzerland Manufacturing GmbH, [name]
Study Device(s)	Anaverse [™] Glenoid System
Study Objectives/Endpoints	The objectives of this study are to confirm safety, performance and clinical benefits of the ASHCOM Shoulder System and its related instruments by analysis of standard scoring systems, radiographs and adverse event records. The primary endpoint is defined by the survival of the implant at 10 years which is based on removal or intended removal of the prosthesis and will be determined using Kaplan Meier method. The safety of the system will be assessed by monitoring the frequency and incidence of adverse events. The secondary endpoint of this study is defined by the
	performance and clinical benefits of the ASHCOM Shoulder System at 5 years, which is assessed by the Constant and Murley score. Assessments of the overall pain, functional performance, survival, quality of life and radiographic parameters of all enrolled study subjects will be evaluated- ed in addition.
Indications/Target Population	Patients suffering from severe shoulder pain and disability indicated for implantation of the ASHCOM Shoulder System and who meet all inclusion and none of the exclusion criteria.
Inclusion/Exclusion Criteria	 Inclusion Criteria: Patient is capable of understanding the doctor's explanations, following his instructions and is able to participate in the follow-up program. Patient has given written consent to take part in the study by signing the "Patient Consent Form". Patient is 18-80 years of age, inclusive. Patient is skeletally mature. Patient requires a primary, fracture or revision reverse total shoulder replacement for the relief of pain and has significant disability due to gross rotator cuff deficiency.

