2 STATISTICAL ANALYSIS PLAN

2.1 Sample Size

This study is designed to have an alpha error no greater than 0.05. Based on an assumed survivorship of 86% at ten years, a sample size of n = 58 at ten years has at least 80% probability to compute a one-sided 95% lower confidence bound on the survivorship of the device with a half-width precision of 0.09. Sample size calculation was computed using SAS 9.4, Proc Power. To account for loss-to-follow-up estimated at 5% per year, 97 patients need to be enrolled in the study to have 58 patients at the end of ten years.

The half-width precision of 0.09 allows us to set a lower bound on survivorship of 9% from the expected survivorship performance of 86% at 10 years. This detectable change of 9% is analogous to non-inferiority margins that approach 10% in regulated studies

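### Does testing the scores without multiplicity adjustment break the stated 0.05 alpha?

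*Combined protocol and SAP*

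**What the plan says.** Three places bear on this point.

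- **Synopsis, Study Objectives/Endpoints.** "The primary endpoint is defined by the survival of the implant at 10 years", analysed by Kaplan-Meier. The secondary endpoint is also single: "performance and clinical benefits of the ASHCOM Shoulder System at 5 years, which is assessed by the Constant and Murley score". Pain, function, quality of life and radiographic findings are listed as further evaluations.
- **SAP section 2.1, Sample Size.** The first sentence is "This study is designed to have an alpha error no greater than 0.05". The next gives the inference for which the study is sized, a "one-sided 95% lower confidence bound on the survivorship of the device with a half-width precision of 0.09".
- **SAP section 2.2, Statistical Analysis.** Score comparisons between the preoperative and follow-up visits are two-sided at 0.05, "with no adjustment for multiple comparisons". The section offers several possible tests. It does not mention the Constant-Murley score or the 5-year visit, and it does not call any comparison descriptive or exploratory.

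**The concern.** The grammatical subject of the alpha sentence is the study, not the primary endpoint. A reader who takes it literally finds, one section later, an open-ended set of further tests, each with its own 0.05. On that reading the stated error rate cannot hold.

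The second worry is selectivity. The synopsis sets out to confirm performance and clinical benefits, and section 2.2 gives the 5-year Constant-Murley comparison no test of its own. A report could then rest a claim of benefit on whichever score and visit happened to be significant. If so, the conclusion on clinical benefit would carry a false-positive risk well above 5%, and the reader would not know it.

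**Working it through.** **1. What the 0.05 is attached to.** The only calculation in section 2.1 is the one for the survivorship bound. Inputs: 86% survivorship, half-width 0.09, n = 58 at ten years, 5% loss per year.

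- Enrolment: 58 / 0.95^10 = 58 / 0.5987 = 96.87, rounded up to 97. This reproduces the plan's figure exactly.
- Evaluable n: 1.96² × 0.86 × 0.14 / 0.09² = 57.1, rounded up to 58, for a two-sided normal-approximation half-width with no probability condition. With the stated one-sided bound and 80% probability, the continuity-corrected version gives 59. The plan does not name the interval type, but that does not bear on multiplicity.

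No score enters this calculation. The bound is one inference on one endpoint, with error 0.05. Adding 15 or 19 score tests leaves that error at 0.05.

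**2. How large the score family might be.** The SAP lists no tests, so the count is an assumption. The synopsis names three scores that plausibly have a preoperative value (Constant-Murley, Oxford, EQ-5D) and five follow-up visits: 3 × 5 = 15. If the surveys at 3 and 7 years carry Oxford and EQ-5D, add 2 × 2 = 4, giving 19.

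**3. Chance of at least one p < 0.05 if no score changes at any visit.** Under independence this is 1 − 0.95^k. The correlated rows come from simulated test statistics with equal correlation; the correlations are assumed.

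| Correlation between tests | 15 tests | 19 tests |
|---|---|---|
| 0 (independent) | 0.537 | 0.623 |
| 0.3 | 0.456 | 0.526 |
| 0.5 | 0.360 | 0.408 |
| 0.7 | 0.254 | 0.284 |
| 0.9 | 0.142 | 0.153 |

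A simulation with a shared baseline (15 tests, visit correlation 0.5, 75 patients, all assumed) gives 0.435, 0.393 and 0.329 for between-score correlations of 0.3, 0.6 and 0.8. A study-wide reading of 0.05 therefore fails under every assumption tried.

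**4. Why those figures overstate the risk of a false benefit claim.**

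- The tests are two-sided, and only the favourable half supports benefit. Under independence this gives 1 − 0.975^15 = 0.316 and 1 − 0.975^19 = 0.382.
- All these figures need no true change in any score at any visit. Patients enter with severe pain and disability and receive a joint replacement, so that is implausible. A comparison with a real improvement cannot falsely show one. If only five comparisons were truly null, say EQ-5D at all five visits, the two-sided figure is 1 − 0.95^5 = 0.226; with three it is 1 − 0.95^3 = 0.143.
- The named secondary endpoint is one score at one time. Tested once, its own error is 0.05.

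**5. Whether the two statements conflict.** Section 2.1 sets 0.05 for the bound that sizes the study. Section 2.2 sets 0.05 for each score comparison and says plainly that the comparisons are not adjusted. Neither claims family-wise control over the scores, so both can be true.

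**The case for a change.** The best case for a change is this. The alpha sentence is not limited to the primary endpoint, nothing labels the score comparisons as descriptive, and the stated aim is to confirm benefit. The one endpoint meant to carry that aim has no designated method in section 2.2, which uses the Oxford score as its example and leaves the test open. Two sentences before analysis would settle the matter at almost no cost.

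Part of this stands. Section 2.2 does not carry the synopsis hierarchy through to a named test, and the scope of the 0.05 has to be inferred from where the sentence sits. The inference is easy, though. A sentence that opens the sample size section and leads straight into a one-sided 95% bound is about that bound. The hierarchy is also already on record, since the synopsis fixes the instrument and the time point and places the other assessments after them. An analyst following both sections would report the 5-year Constant-Murley change as the secondary result and the rest as supporting.

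Selective reporting remains possible, but the documents tie no success criterion to any score p-value, and the lack of adjustment is disclosed to whoever reads the results.

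**Conclusion.** The concern does not call for a change. The 0.05 in section 2.1 is best read as the error rate of the one-sided bound on 10-year survivorship, and the score tests leave it untouched. The family-wise figures of 0.14 to 0.62 are arithmetically sound, but they rest on an assumed 15 to 19 tests, assumed correlations and a null of no change anywhere after shoulder replacement. They also measure a guarantee that the plan does not give.

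What remains is a small gap in wording that analysts can fill from the synopsis. Stating the scope of the alpha, naming the 5-year Constant-Murley change in section 2.2 and calling the other comparisons descriptive would be a reasonable optional clarification. It would relabel results without altering any estimate, test, sample size or primary conclusion. Whether disclosed, unadjusted secondary comparisons in a non-controlled post-market study need such labels is a matter on which careful statisticians differ.

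This conclusion depends on the contextual reading of the alpha sentence and on the absence of any decision rule based on scores. It would change if a claim of clinical benefit were made to depend on any significant score at any visit.
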